6.3 Visit 3 – First ketamine infusion

On the day of each infusion, participants will arrive at the University of Minnesota Masonic Children's Hospital - Journey Clinic infusion center. Adolescent participants who are currently inpatient on the adolescent psychiatric ward will be escorted to the Journey clinic by hospital staff (four floors up the elevator). Adolescent participants who are outpatient will arrive at the Journey Clinic with their parent or guardian. An indwelling catheter will be placed in the non-dominant arm for ketamine administration and for two blood draws at the first infusion visit.

At this visit, directly before the ketamine infusion, participants will have 20 cc of blood drawn into heparinized tubes. They will have a second blood draw two hours after the infusion is complete. The blood samples will be sent to [name] at the Mayo Clinic for analysis.

Subjects will receive IV infusion of 0.5 mg/Kg of ketamine hydrochloride over 40 minutes. Digital pulse oximetry, respiratory rate, heart rate and blood pressure will be recorded every 15 minutes throughout the infusion, beginning 15 minutes before infusion. Vital signs will be monitored for at least 2 hours post infusion, to be assured there are no lingering side effects before leaving the unit.

Prior to infusion, participants will be asked to complete the BDI-II, SHAPS, TEPS and POMS-A, and a trained member of research staff will complete the Clinical Global Impressions Scale (CGI) (Guy, 1976), BPRS+, MADRS, CADSS. At the end of the infusion and 1 hour post infusion, participants will be asked to complete SHAPS, TEPS and POMS-A, and a trained member of research staff will complete BPRS+ and CADSS. At 2 hours post infusion, participants will be asked to complete the BDI-II, MADRS, SHAPS, TEPS and POMS-A, and a trained member of research staff will complete the Clinical Global Impressions Scale (CGI) (Guy, 1976), BPRS+, MADRS, CADSS.

If adolescent reports experiencing nausea or vomits during the infusion or the subsequent 2-hour observation period, the PI will evaluate the adolescent's reported symptoms and determine if (a) P.R.N. Ondansetron is indicated at that time (0.15mg/kg, up to 8mg), and (b) pre-treatment with IV Ondansetron for control of nausea is warranted for the subsequent infusions.

Participants will be asked about any adverse events (AE) and concomitant medications at each visit.

To be discharged from the infusion unit, the adolescent must meet the following discharge criteria:

CONFIDENTIAL

- 1) Stable vital signs
- 2) Pain is under control
- 3) A return to the level of consciousness that is similar to the baseline for that patient
- 4) Adequate head control and muscle strength to maintain a patent airway
- 5) Nausea and/or vomiting is not present
- 6) The patient is adequately hydrated.

After each infusion, adolescents will either return to the inpatient unit escorted by hospital staff, or if they are outpatient, will return home escorted by their parent(s). Participants (and parents if outpatient, or hospital staff if inpatient) will receive written discharge instructions regarding rare but serious side effects from ketamine and several measures to improve recovery at home.

6.4 Visits 4-8 – 5 subsequent ketamine infusions

Participants will undergo a total of six ketamine infusions within a 2-week period (on a Monday-Wednesday-Friday schedule). The 5 subsequent treatments will be conducted in the same way the first treatment was conducted (please see section 6.3 for details), except the blood draw only occurs before the first and after the last infusion.

After the conclusion of the 6th ketamine infusion (after participants has past the “2 hour post infusion” time point during the 6th clinic visit). Participants will again have 20cc of blood drawn by venipuncture, which will be handled in the same way as other blood draws (see section 6.3 for further details).

If adolescent has experienced nausea or vomited during any prior infusion and PI has determined that pre-treatment with IV Ondansetron is appropriate for management of adolescent’s nausea symptoms, adolescent will receive IV Ondansetron at a dose of 0.15 mg /kg (up to 8 mg) via the same IV port established for infusion of ketamine immediately before the administration of ketamine.

6.5 Visit 9 – Second brain MRI

Within 1 week of the last ketamine infusion, participants will undergo another brain MRI identical to the previous one (please see section 6.2 for more details).

6.6 Visit 10 – Clinical assessment and blood draw

Also within one week of the last ketamine infusion, participants will come to the Ambulatory Research Center or participate in a phone or video conference for clinical evaluation to assess their clinical response to the ketamine infusions. At this visit, the following assessments will be completed to determine response to treatment: Columbia Suicide Severity Rating Scale – Since Last Visit (CSSRS-SLV), Montgomery-Asberg Depression Rating Scale (MADRS), Clinician-Administered Dissociative States Scale (CADSS), Profile of Mood States-Adolescent Version (POMS-A), Snaith-Hamilton Pleasure Scale (SHAPS), Temporal Experience of Pleasure Scale (TEPS), Beck Depression Inventory-II (BDI-II), Clinical Global Impression (CGI), and Brief Psychiatric Rating Scale (BPRS). Also, the clinician will complete a Children’s Depression Rating

CONFIDENTIAL

Scale-Revised, a clinical interview with both adolescent and parent/guardian (separately), to assess depression severity. The participant will also be asked to perform the DPX-task.

6.7 Visits 11-16 – Follow-up period

All participants will be asked to speak with the research team for weekly follow-up visits for 6 weeks. Participants will continue to take medications as prescribed by their doctor. At each of these visits, participants will be asked about any medication changes and will complete the same assessments as administered in visit 10 (MADRS, CADSS, POMS-A, SHAPS, TEPS, BDI-II, CGI, CDRS and BPRS).

All participants will be asked to participate in the 6 weekly follow-up visits, regardless of response.

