3.2 Primary Study Endpoints

The primary outcome measure is response status as defined by Children's Depression Rating Scale (CDRS) (Poznanski, 1985) Responders will be defined as having a significant reduction in their CDRS score ($\geq 50\%$) whereas non-responders will be defined as subjects whose scores do not show such a significant reduction or whose score increase. The percent change will be calculated by the formula below (Tao, 2009):

$$(\text{Baseline CDRS} - \text{Exit CDRS}) / (\text{Baseline CDRS} - 17)$$

Baseline CDRS: CDRS score obtained on Visit 1 – Baseline Assessment (Section 6.1)
Exit CDRS: the latest CDRS score obtained on Visit 10 - Clinical Assessment (Section 6.6) or Visit 11-16 – Follow-up Period (Section 6.7)

CONFIDENTIAL

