4.4 Early Withdrawal of Subjects

When and How to Withdraw Subjects

A subject may be withdrawn from the study prior to expected completion for the following reasons:

- Participant experiences adverse side effects to the ketamine treatments that are intolerable to the adolescent or the parent.
- Participant fails to adhere to protocol requirements
- Participant or participant's parent(s) withdraw consent

If a subject exits the study for any reason (withdrawal, non-response, or relapse), he or she will continue his or her pre-study regimens and consult with his or her psychiatrist about the next step in treatment.

Data Collection and Follow-up for Withdrawn Subjects

For all participants, we will request permission during the consent process to collect naturalistic follow-up data through in person visit to clinic or video conference 6 months after the 6-week study period.

The naturalistic follow-up encounter will be as follows:

We will ask permission to contact the family to inquire about the participant. Subjects will be determined lost to follow-up if they do not respond to 4 e-mails to the primary e-mail address of parent(s) or 4 phone calls to their primary number or to their next-of-kin, or to a certified letter.

During the follow up in person visit to clinic or video conference subject will be asked to provide:

- a) A narrative interval history including following elements
 - a. Changes in medications and their effects
 - b. Therapies or other treatments they have undergone and their effects
 - c. Evolution of their symptoms during the interval
 - d. Any hospitalizations including cause and outcome
 - e. Any suicide attempts including precipitating factor (if any) and outcome
- b) Participate in a clinical interview in order for clinician to complete an assessment using CDRS-R, CADSS, CGI, and MADRS.
- c) Complete the BDI-II, Profile of Mood States – Adolescent, SHAPS and TEPS

5 Study Drug

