5.5 Subject Compliance Monitoring

Since the study medication is administered in an infusion unit, compliance with study medication will be measured by whether participants present to infusion visits and cooperate with all procedures of IV ketamine administration. To be compliant with other aspects of the study, participants will be required to attend two MRI scans, six ketamine treatment visits and six weekly follow-up visits. The follow up visits may take place in person or, for subjects who do not reside within convenient travel distance to Minneapolis, via phone or video conference. Study staff will monitor whether the participant is attending these visits. If a participant is not compliant with study procedures, his/her participation in the study will be terminated.

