5.6 Prior and Concomitant Therapy

CONFIDENTIAL

If present, current antidepressant treatment (pharmacological, augmenting agents, and non-pharmacological) must be dose stable for at least 2 months prior to beginning the study. Patients will continue with current antidepressant treatment throughout the study. Based on our experience in current research at the VA Medical Center using serial ketamine dosing (Shiroma 2013), patients have shown positive results while continuing their current antidepressant treatment.

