7.3 Statistical Methods

In the following analyses, primary outcome measures will include the “per protocol” population. The secondary measures will include the “intent to treat” population.

Primary analysis: Paired t tests will be conducted between the lowest score from the post-treatment assessments and the baseline symptom levels to assess the maximum effect of ketamine infusion on symptoms for each person.

Secondary Analyses:

1. We will calculate the time to relapse for each participant.
2. Biological Mechanisms:
 - a. Neuroimaging data: Paired t tests will be conducted to evaluate pre- and post ketamine treatment changes in measures of brain functional activation, connectivity, white matter microstructure and brain metabolite concentrations. These preliminary data will be used to identify responsive measures and estimate sample sizes that would be needed to use these measures as endpoints in future studies.
 - b. Bimolecular studies to examine mechanisms of cellular resilience (insulin challenge, cytokine testing, gene expression) will be conducted to evaluate change in these pathways before and after ketamine. Analyses will be conducted by [name] at Mayo Clinic. Peripheral blood mononuclear cells (PBMCs) will be isolated from whole blood and divided into two groups. The first group will not receive any treatment. RNA will be extracted and whole genome microarray will be performed using illumina's genome-wide gene expression arrays. Differential pre- versus post-ketamine mRNA levels will be quantified and bioinformatics pathway analysis will be used to identify key differences in molecular responses to ketamine. A second subset of PBMCs will be cultured and cryopreserved. Once all samples are collected cells will be immortalized to ensure sufficient tissue availability. The following two separate analyses will then be performed:

CONFIDENTIAL

- i. Group 1 PBMCs will be stimulated with insulin and intracellular Akt, mTOR, and GSK3 gene and protein levels will be quantified following 0, 5, 15, and 30 minutes of stimulation. This signaling pathway is implicated in mediating the antidepressant response to ketamine. Western blot and rtPCR techniques will be used to quantify protein and gene expression, respectively;

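### Exit CDRS is the latest score up to follow-up week 6, so improvement after a doctor's medication step-up can be counted as ketamine response

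*Combined protocol and SAP*

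**What the plan says.** **Medication in follow-up.** Section 6.7 states: "Participants will continue to take medications as prescribed by their doctor. At each of these visits, participants will be asked about any medication changes". It also keeps everyone under observation: "All participants will be asked to participate in the 6 weekly follow-up visits, regardless of response".

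**Intended background treatment.** Section 5.6, like 5.2, says: "Patients will continue with current antidepressant treatment throughout the study". The two-month dose-stability requirement applies only before study entry. Section 4.4 says that a subject who leaves for withdrawal, non-response or relapse stays on the pre-study regimen and discusses further treatment with his or her psychiatrist.

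**Compliance.** Section 4.4 lists as a ground for withdrawal: "Participant fails to adhere to protocol requirements". Section 5.5, which is mainly about attendance, adds: "If a participant is not compliant with study procedures, his/her participation in the study will be terminated".

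**Response.** In Section 3.2 the Exit CDRS is "the latest CDRS score obtained on Visit 10" or on any of Visits 11 to 16, and a reduction of at least 50% makes a responder. Section 6.6 says of Visit 10: "At this visit, the following assessments will be completed to determine response to treatment". The CDRS-R is completed at that visit.

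**Primary test.** Section 7.3 says: "Paired t tests will be conducted between the lowest score from the post-treatment assessments and the baseline symptom levels". It names no scale, no last visit and no rule for medication changes.

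**The concern.** The trial has one arm, so nothing in the design separates the effect of a drug started or increased in follow-up from the effect of ketamine. Any separation has to come from the endpoint rule. The rule in Section 3.2 works the other way: it takes the score furthest from the last infusion, after the longest opportunity for a treating doctor to act on a poor result.

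The participants most likely to be stepped up are those who have not done well. If the new treatment helps by week 6, they move from non-responder to responder on the primary outcome. Stopping or reducing a drug could move scores in the opposite direction, and the plan does not handle that either. Medication changes are asked about every week, but no endpoint, population or analysis in Sections 3.2, 3.3 or 7.1 to 7.3 uses the answers.

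**Working it through.** The sample size of 20 has no stated alpha, power, effect size or standard deviation, so there is no plan figure to reproduce. The point does not depend on one.

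**Which scores can decide response.** Sections 6.3 and 6.4 do not list the CDRS at the infusion visits. Within the main study, the post-treatment CDRS scores come from Visit 10 (6.6) and Visits 11 to 16 (6.7). Six of these seven visits fall in the period when the treating doctor prescribes.

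**Classification.** The formula in Section 3.2 is (baseline − exit) / (baseline − 17). The scores below are illustrative.
- With baseline 60, the denominator is 60 − 17 = 43. Response requires an exit score of at most 60 − 0.5 × 43 = 38.5.
- Visit 10 score 50: (60 − 50)/43 = 10/43 = 23.3%, a non-responder.
- A new drug is started, and the week-6 score is 38: (60 − 38)/43 = 22/43 = 51.2%, a responder.

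**Size per participant.** One reclassified participant is 1/20 = 5.0 percentage points. Section 7.2 limits the primary analysis to those who complete six infusions. If only 15 did so (assumed), one participant would be 1/15 = 6.7 points.

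**How many participants.** Let p be the true Visit 10 response rate, q the share of non-responders stepped up, and r the share of those who reach response by the last visit. The expected excess is 20 × (1 − p) × q × r. None of these values is in the documents. Over assumed ranges of p from 20% to 60%, q from 10% to 50% and r from 20% to 40%:
- lowest: 20 × 0.4 × 0.1 × 0.2 = 0.16 participants, or 0.8 points
- highest: 20 × 0.8 × 0.5 × 0.4 = 3.2 participants, or 16 points

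This spread shows that the documents do not determine the size. It is not an estimate.

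**Effect of the choice of score.** A simulation assumed no ketamine effect, n=20, mean 60, SD 10, correlation 0.7, and a step-up acting from follow-up week 3. With 10% to 50% of participants stepped up and a benefit of 8 to 15 points:

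| Score used | Apparent mean improvement, no step-up | With step-up |
|---|---|---|
| Visit 10 | about 0 | about 0 |
| Latest | about 0 | 0.8 to 7.5 |
| Lowest of seven | 7.4 | 8.1 to 14.0 |

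Visit 10 is unaffected because the assumed step-ups come later. For the lowest score, selecting the minimum accounts for 7.4 points by itself. Step-up adds 8.07 − 7.39 = 0.7 to 14.04 − 7.39 = 6.7 points, which is less than the selection effect in every setting. In the worked example, one participant whose lowest score falls from 50 to 38 adds (50 − 38)/20 = 0.6 point to the mean change.

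**The case against.** **Changes are not intended.** Sections 5.2 and 5.6 have current antidepressants continuing throughout, and 6.7 can be read as plain continuation. On one reading of 4.4, the next treatment step comes only after study exit, so the latest CDRS would precede it. This has some force, and that doctors may change medication is an inference from text in tension with itself. But continuing one drug does not rule out adding another or raising a dose. Section 6.7 asks weekly about changes and asks non-responders to keep attending. The compliance clauses do not make a doctor's prescription a breach, and they remove no scores.

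**The as-written rule is the stricter one.** A week-6 score counts relapse against ketamine, and a Visit 10 score does not. This stands. A reader might infer that the latest-score rule inflates the response rate overall. The documents do not support that: relapse pulls the rate down, step-up pushes it up, and the net direction is unknown.

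**Half the sample is at risk.** A reader might combine the adult figures in Section 1.4 (90% cumulative response, 50% not relapsed at 4 weeks) and conclude that 10 or 11 of 20 would be out of response and open to reclassification. That does not follow. Relapse in Section 3.3 is a CDRS of at least 50% of baseline, which is 30 when baseline is 60, while response under 3.2 holds up to 38.5. Scores from 30 to 38.5 therefore satisfy both definitions. The adult study's relapse definition is not given, and its figure is at 4 weeks. For the same reason, a responder who rises to 45 and falls back to 37 after a step-up has not recovered under 3.3, although 3.2 would class that participant as a responder. The 38 in the worked example also lies in this overlap. The example does not depend on it, because any week-6 score of 38.5 or below, including one under 30, reverses the classification.

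**The t test.** A reader might take step-up to be a main threat to the Section 7.3 result. The section names neither scale nor window, and 3.1 also lists assessments in the hours after infusion. That follow-up CDRS scores enter the minimum is the natural reading, but it is not stated. In the simulation the effect is smaller than that of selecting the minimum, which is a separate matter.

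**Conclusion.** The point holds for the primary outcome. It rests on a stated rule and not only on an omission: Section 3.2 explicitly extends Exit CDRS to Visit 16, across a period in which 6.7 leaves medication to the treating doctor. Nothing bars a step-up or sets aside later scores. Each Visit 10 non-responder who reaches response after a step-up adds 5 percentage points at n=20. How many there would be cannot be estimated, because the documents give no rate of medication change. Participants have also failed to remit on at least two antidepressant trials, so success on another drug should not be assumed to be common.

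For the t test the point is secondary and depends on how 7.3 is read. Overall this is a worthwhile, inexpensive correction to the endpoint definition. It is not evidence that the study's result would be wrong, and it takes no position on whether medication should be allowed to change.

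**What to change.** 1. **Section 3.2.** Determine response from the Visit 10 CDRS, in line with 6.6, and flag anyone stepped up before that visit. If the sponsor prefers a later time point, the minimum change is to use the latest CDRS before any start or increase of antidepressant or augmenting treatment. This keeps relapse before a step-up in the outcome, at the price of differing assessment times.
2. **Weekly visits.** Record the date and nature of each medication change. Sections 6.3 and 6.7 say that participants are asked about medications and changes, but they do not say that dates are collected.
3. **Reporting.** Give the as-written latest-score response rate alongside, with the number and timing of medication changes.
4. **Section 7.3.** Add one sensitivity analysis of the lowest-score t test that excludes scores after a step-up. Those participants then have fewer scores from which to take a minimum, which is a reason not to make it the main analysis.

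The cost is wording plus a date field, with no new visits. The downside is that a Visit 10 rate says nothing about later relapse. On the adult experience in Section 1.4 it will probably be higher than the week-6 rate, so it should always be reported together with the relapse endpoint and the as-written rate.

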6.8 Schedule of Events Table

| | Consent | Interview | Questionnaires in-person | MRI | Blood draw | Ketamine infusion |
|---|---------|-----------|--------------------------|-----|------------|-------------------|
| Initial visit | X | X | X | | | |
| Within a week from first visit | | | | X | X | |
| Week 1 *Monday | | | | | | X |
| Week 1 Wednesday | | | | | | X |
| Week 1 Friday | | | | | | X |
| Week 2 Monday | | | | | | X |
| Week 2 Wednesday | | | | | | X |
| Week 2 Friday | | | | | | X |
| Within a week from last infusion | | X | X | X | X | |
| Follow-Up Week 1 | | | X | | | |
| Follow-Up Week 2 | | | X | | | |
| Follow-Up Week 3 | | | X | | | |
| Follow-Up Week 4 | | | X | | | |
| Follow-Up Week 5 | | | X | | | |
| Follow-Up Week 6 | | | X | | | |

*The Monday, Wednesday, Friday schedule does not have to start on a Monday, it can start on a Wednesday or Friday, but treatments will always occur on these days and the total time will always be 2 weeks.

CONFIDENTIAL

This material is the property of the University of Minnesota. Do not disclose or use except as authorized in writing by the study sponsor

7 Statistical Plan

7.1 Sample Size Determination

In view of the lack of any reports on ketamine in adolescent depression, the study sample was based on published studies in adult depression.

7.2 Subject Population(s) for Analysis

Data from each participant who completes the six ketamine treatments will be subjected to the primary study analysis. We will conduct secondary analyses on all participants who received at least one dose of treatment.

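### The primary efficacy analysis keeps only participants who complete all six infusions, which probably overstates efficacy because early leavers drop out of the headline result

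*Combined protocol and SAP*

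**What the plan says.** The population is set in two places. Section 7.2: "Data from each participant who completes the six ketamine treatments will be subjected to the primary study analysis". Section 7.3: "In the following analyses, primary outcome measures will include the" per protocol population, with the intent-to-treat population assigned to secondary measures. Section 7.2 also promises secondary analyses of everyone given at least one dose. The secondary analyses that 7.3 goes on to list, however, are time to relapse and biological mechanisms; CDRS response in all treated participants is not among them. No rule for missing outcomes is given.

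Sections 4.4 and 5.5 describe how people leave. Among the withdrawal reasons in 4.4 is: "Participant experiences adverse side effects to the ketamine treatments that are intolerable to the adolescent or the parent". Failure to adhere and withdrawn consent are also listed, and a later sentence in 4.4 begins: "If a subject exits the study for any reason (withdrawal, non-response, or relapse". Section 5.5 adds: "If a participant is not compliant with study procedures, his/her participation in the study will be terminated".

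On outcome data, section 3.2 defines the exit score as "the latest CDRS score obtained on Visit 10 - Clinical Assessment" or at Visits 11-16. Section 6.3 lists the scales for infusion visits, for example: "At 2 hours post infusion, participants will be asked to complete the BDI-II, MADRS, SHAPS, TEPS and POMS-A". CDRS is not among them. Section 6.7 states: "All participants will be asked to participate in the 6 weekly follow-up visits, regardless of response".

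**The concern.** Completing six infusions is something that happens after treatment begins and can depend on how treatment goes. Selecting the primary set on it conditions the efficacy estimate on tolerating the regimen and staying with it. In a controlled trial a similar selection might operate in both arms; here there is one open-label group of 20, so nothing offsets it.

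Two of the exit reasons in 4.4, intolerable side effects and non-response, make it plausible that leavers improve less than completers. The headline would then describe those who finished, while the primary objective in section 2 concerns adolescents with treatment-resistant depression generally. Section 5.2 says a randomised placebo-controlled trial is to follow, and an inflated effect size from this pilot could be carried into its planning.

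The data problem compounds the population problem. Because the exit score exists only from Visit 10 onward, someone who stops after, say, two infusions has a usable CDRS outcome only if seen at those later visits, and the documents do not settle whether they would be.

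**Working it through.** **Is there any route back into the primary result?**

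- Sections 7.2 and 7.3 agree with each other, and no other section returns early leavers to the primary analysis.
- People terminated after infusion six, for instance for missing the second MRI or a follow-up visit, have completed the infusions and stay in the set as 7.2 defines it. The exclusion concerns those who leave after infusion one and before infusion six.
- Section 4.4 speaks of exit for non-response, 5.5 ends participation for non-compliance, and 6.7 asks all participants to attend follow-up whatever their response. These do not give one answer on whether an early leaver is assessed at Visits 10-16.
- The six-month naturalistic contact in 4.4 includes a CDRS-R, but it falls outside the window that 3.2 allows for the exit score.

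**How large could the distortion be?** The plan has no figure to reproduce: section 7.1 bases N = 20 on adult studies and gives no dropout, response rate or standard deviation. What follows is illustrative. Inputs: N = 20 (section 3.1); the number of early leavers k and their outcomes are assumptions.

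*Response endpoint (section 3.2).* Take k = 4 and 10 responders among 16 completers.

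| Result | Calculation | Rate | Clopper-Pearson 95% CI |
|---|---|---|---|
| Completers, as planned | 10/16 | 62.5% | 35.4% to 84.8% |
| All treated, 0 of 4 leavers respond | 10/20 | 50% | 27.2% to 72.8% |
| All treated, 1 of 4 responds | 11/20 | 55% | 31.5% to 76.9% |
| All treated, 2 of 4 respond | 12/20 | 60% | 36.1% to 80.9% |

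With leavers counted as non-responders, the gap is the completer rate times k/20: 0.625 × 4/20 = 0.125. The direction reverses if leavers do better than completers; if all 4 respond, the all-treated rate is 14/20 = 70%. The intervals overlap widely, so the point is bias, not a significant difference between sets.

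*Mean change (the paired test in section 7.3).* Let c be the leavers' mean change as a fraction of the completers'. The ratio of completer mean to all-treated mean is 1/(1 − (k/20)(1 − c)).

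| k | c = 0 | c = 0.5 | c = 1 |
|---|---|---|---|
| 2 | 1/0.90 = 1.11 | 1/0.95 = 1.05 | 1.00 |
| 4 | 1/0.80 = 1.25 | 1/0.90 = 1.11 | 1.00 |
| 6 | 1/0.70 = 1.43 | 1/0.85 = 1.18 | 1.00 |

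*Does the test result change?* Assume a completer mean change of 1.0 SD and k = 4 with no change.

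- Completers: t = 1.0 × √16 = 4.00.
- All treated: mean = 16 × 1.0/20 = 0.80. Sum of squares = 15 + 16(0.2)² + 4(0.8)² = 15 + 0.64 + 2.56 = 18.2. SD = √(18.2/19) = 0.979. Standardised effect = 0.80/0.979 = 0.82. t = 0.80/(0.979/√20) = 3.66.

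The test statistic barely moves; the reported effect size does.

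**The case against.** The strongest reply has four parts.

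**Direction is inferred.** The bulleted withdrawal reasons in 4.4 are intolerance, non-adherence and withdrawn consent; non-response appears only in the sentence that follows. Sections 6.4 and 6.6 suggest that everyone is meant to have six infusions and that response is judged afterwards, so a non-responder identified at Visit 10 is still a completer. The documents do not say that intolerance goes with poor response. This stands as a reason for saying likely and not certain. It does not make completion unrelated to treatment, since intolerance alone ties the two together.

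**An all-treated analysis is already planned.** True, and if it covered CDRS response the reader would see both results and the issue would be mostly one of labelling. But 7.3 names only time to relapse and biological measures as secondary analyses, so that is not assured.

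**Sections 5.5 and 6.7 can both be true.** One concerns compliance and the other response. That is a fair reading of those two alone. It still leaves follow-up of people who stop infusions early unresolved, and an exit for non-response in 4.4 does not fit with asking everyone to attend regardless of response.

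**The sizes are assumed.** Treatment lasts two weeks and dropout may be low. The largest ratios need leavers with no change at all. Section 7.3 uses each person's lowest score and names no scale, so if infusion-visit MADRS or BDI-II counted, leavers might show some improvement. All of this stands, and it is why a range down to zero is shown.

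**Conclusion.** The concern holds. The plan explicitly restricts its primary efficacy result to six-infusion completers, has no specified CDRS analysis that brings early leavers back, and has no missing-outcome rule. The restriction is certain from the text. That it overstates efficacy is probable and rests on leavers improving less than completers.

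Under assumed early stopping of 2 to 6 of 20, the completer mean change exceeds the all-treated mean by 11% to 43% if leavers do not change, by 5% to 18% if they improve half as much, and not at all if they improve equally or if nobody stops. The distortion lies mainly in the size of the reported effect; the paired-test conclusion may hardly be affected. This should be changed, because the remedy is cheap and the effect estimate is what a pilot hands on.

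**What to change.** 1. Make everyone who received at least one infusion the primary population for CDRS response. Count a missing Exit CDRS as non-response. Keep six-infusion completers as a supportive analysis.
2. Run the continuous CDRS analysis in the same all-treated set, with a sensitivity analysis that sets missing outcomes to no change from baseline. A mixed model alone cannot correct for people who have no post-baseline CDRS: it would rest on the assumption that they resemble those who were observed, which is the point in doubt.
3. Use the infusion-visit MADRS and BDI-II as supporting data for early leavers.
4. Reconcile 4.4 and 5.5 with 6.7 on data collection only, so that consenting participants who stop early, for whatever reason, still have CDRS collected at Visits 10-16. Phone or video contact is already allowed in 5.5 and 6.6.
5. Report the number of non-completers and their reasons.

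The cost is SAP wording, a short clarification of three protocol sections and a few extra remote assessments. The stated result may be somewhat less favourable, and counting missing as non-response is conservative if some leavers did respond; item 4 limits how often that rule is needed. Nothing here alters dosing or the rules for stopping infusions.
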